2.4.5.1 Analyses of adverse events

Generalities

The primary focus of AE reporting will be on TEAEs. Pre-treatment and post-treatment AEs will be described separately.

If an AE date/time of onset (occurrence, worsening, or becoming serious) is incomplete, an imputation algorithm will be used to classify the AE as pre-treatment, or TEAE, or post-treatment AE. The algorithm for imputing date/time of onset will be conservative and will classify an AE as treatment-emergent unless there is definitive information to determine it is pre-treatment or post-treatment. Details on classification of AEs with missing or partial onset dates are provided in [Section 2.5.3](#).

Adverse event incidence tables will present by SOC, HLGT, HLT, and PT, sorted in SOC internationally agreed order and then alphabetical order, and present the number (n) and percentage (%) of patients experiencing an AE by treatment group. Multiple occurrences of the same event in the same patient will be counted only once in the tables within a treatment phase. The denominator for computation of percentages is the safety population within each treatment group.

The tables by primary SOC and PT will be sorted by internationally agreed order of SOC and decreasing frequency of PT within SOC. Sorting will be based on results for the sarilumab 200mg arm.

Analysis of all treatment-emergent adverse events

The following TEAE summaries will be generated for the safety population.

- Overview of TEAEs, summarizing number (%) of patients with any
 - TEAE
 - Serious TEAE
 - TEAE leading to death
 - TEAE leading to permanent treatment discontinuation
- All TEAEs by primary SOC, HLGT, HLT, and PT, showing number (%) of patients with at least one TEAE sorted by SOC internationally agreed order. The other level (HLGT, HLT, PT) will be presented in an alphabetic order.
- All TEAEs by primary SOC and PT, showing number (%) of patients with at least one TEAE, sorted by SOC internationally agreed order and decreasing incidence of PTs within SOC. This sorting order will be applied to all other tables, unless otherwise specified.
- All TEAEs by primary SOC, showing number (%) of patients with at least one TEAE, sorted by internationally agreed order of primary SOC.

- All TEAEs by relationship, presented by primary SOC, HLG, HLT, and PT, showing number (%) of patients with at least one TEAE, sorted by SOC internationally agreed order. The other level (HLG, HLT, PT) will be presented in an alphabetic order.
- All TEAEs by maximal severity, presented by primary SOC and PT, showing number (%) of patients with at least one TEAE by severity (ie, mild, moderate, or severe), sorted by sorting order defined above.

Analysis of all treatment emergent serious adverse event(s)

- All treatment-emergent SAEs by primary SOC, HLG, HLT, and PT, showing number (%) of patients with at least one serious TEAE, sorted by SOC internationally agreed order. The other level (HLG, HLT, PT) will be presented in an alphabetic order.
- All treatment-emergent SAEs by primary SOC and PT, showing number (%) of patients with at least one TEAE
- All treatment-emergent SAEs by primary SOC, showing number (%) of patients with at least one TEAE, sorted by internationally agreed order of primary SOC

Analysis of all treatment-emergent adverse event(s) leading to treatment discontinuation

- All TEAEs leading to treatment discontinuation, by primary SOC, HLG, HLT, and PT, showing number (%) of patients sorted by SOC internationally agreed order. The other level (HLG, HLT, PT) will be presented in an alphabetic order.
- All TEAEs leading to treatment discontinuation, by primary SOC and PT, showing number (%) of patients with at least one TEAE
- All TEAEs leading to treatment discontinuation, by primary SOC, showing number (%) of patients with at least one TEAE, sorted by internationally agreed order of primary SOC

Analysis of all treatment-emergent adverse event(s) leading to dose reduction

- For the management of pre-defined laboratory abnormalities, sarilumab dose can be reduced to 150 mg q2w. All treatment-emergent adverse events leading to dose reduction, by primary SOC, HLG, HLT and PT, showing the number (%) of patients, sorted by the sorting order defined above

Analysis AESI

- Summaries of AESI defined by the search criteria:
 - All treatment-emergent AESIs, by AESI category and PT, showing number (%) of patients, sorted by decreasing incidence of PT within each AESI category.
 - Within each treatment-emergent AESI category, at a minimum the data display will include:
 - Overview summary
 - Treatment duration summary
 - Incidence by patient and by event

- Serious TEAEs
- TEAEs leading to treatment discontinuation
- TEAEs leading to death
- Possibly related TEAEs

2.4.5.2 Deaths

The incidence of death will be generated on the safety populations.

- Number (%) of patients who died by study period (on-treatment, treatment residual, and post-treatment).
- Death in non-randomized patients or randomized but not treated patients.
- TEAE leading to death (death as an outcome on the AE CRF page as reported by the Investigator) by primary SOC and PT, showing number (%) of patients sorted by internationally agreed order of SOC and decreasing frequency of PT within a SOC in the Sarilumab 200mg q2w treatment group.

Listings will be provided for all deaths with flags indicating during treatment or post-treatment status.

2.4.5.3 Analyses of laboratory variables

The summary statistics (including number, mean, median, SD, minimum and maximum) of all laboratory variables (central laboratory values and changes from baseline) will be calculated for each visit or study assessment (baseline, each post baseline time point, endpoint) by treatment group. This section will be organized by biological function as specified in [Section 2.1.4.3](#).

In addition, for all laboratory parameters, the mean value and mean change from baseline at each scheduled visit during the treatment period will be plotted by treatment group.

The incidence of PCSAs (list provided in [Appendix B](#)) at any time during TEAE period will be summarized by biological function and treatment group whatever the baseline level and/or according to the following baseline status categories:

- Normal/missing
- Abnormal according to PCSA criterion or criteria

For lipids, the National Cholesterol Education Program Adult Treatment Panel III (NCEP ATPIII) classification will be used for the baseline.

The incidence of abnormal laboratory values at any time during the TEAE period will be summarized in shift tables by biological function and treatment group whatever the baseline level and/or according to the following baseline status categories:

- Normal/Missing

- Abnormal high according to the normal range
- Abnormal low according to the normal range

Time to onset of the initial LDL-C elevation (≥ 4.1 mmol/L, ≥ 4.9 mmol/L), time to onset of the initial total cholesterol elevation (≥ 6.2 mmol/L), time to onset of the initial Grade 3 or Grade 4 neutropenia (neutrophil count < 1.0 Giga/L), time to onset of the initial platelet count < 100 Giga/L, time to onset of the initial lymphocyte count < 1.0 Giga/L, time to onset of the initial ALT elevation (> 3 x ULN, > 5 x ULN), time to onset of the initial AST elevation (> 3 x ULN, > 5 x ULN), and time to onset of initial total bilirubin > 2 x ULN will be analyzed using Kaplan-Meier estimates, using the midpoint of the time interval between the first assessment showing the elevation and the previous assessment, presented by treatment group.

Listings will be provided with flags indicating the out of range values as well as the PCSA values.

Neutrophils

The incidence of neutropenia by maximal grade (lowest absolute neutrophil count reported during the TEAE period) will be summarized. The 4 grades are defined as below:

- Grade 1: ≥ 1.5 Giga/L-LLN.
- Grade 2: ≥ 1.0 Giga/L- < 1.5 Giga/L.
- Grade 3: ≥ 0.5 Giga/L- < 1.0 Giga/L.
- Grade 4: < 0.5 Giga/L.

Thrombocytopenia

The incidence of thrombocytopenia by maximal grade (lowest platelet count reported during the TEAE period) as defined below will be summarized.

- ≥ 75 Giga/L-100 Giga/L.
- ≥ 50 Giga/L- < 75 Giga/L.
- ≥ 25 Giga/L- < 50 Giga/L.
- < 25 Giga/L.

Hepatic disorders

The liver function tests, namely AST, ALT, ALP, and total bilirubin are used to assess possible drug-induced liver toxicity. The proportion of patients with PCSA values at any post-baseline visit by baseline status will be displayed by treatment group for each parameter. The proportion of patients with PCSA values at any post baseline visit may be displayed by duration of exposure for each treatment group.

A graph of distribution of peak values of ALT versus peak values of total bilirubin will also be presented. Note that the ALT and total bilirubin values are presented on a logarithmic scale. The

graph will be divided into 4 quadrants with a vertical line corresponding to 3x ULN for ALT and a horizontal line corresponding to 2x ULN for total bilirubin.

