
ASSESSMENT SCHEDULE
	
The study will consist of the following visits:
 
 • Visit 1 (D -42 - D -1): Screening • Visit 2 (D1): Baseline, randomization, first study drug administration • Visit 2 to 12 (D1-Week 52): on treatment (double-blind phase) • Visit 12 (Week 52): End of Treatment (EOT) visit (last sarilumab or matching placebo administration at Week 50) • Visit 13 (Week 58): 6 weeks post-treatment follow up visit • Visit 14 (Week 76): EOS visit 
Patient's CS tapering period may vary (maximum of 52 weeks) depending on the dose of daily prednisone at the time of randomization.
 
At screening and baseline visits, a physical examination to assess disease activity and general health will be performed. Patients will be assessed for active or latent tuberculosis (TB) at baseline and during the study. Laboratory tests includes hematology, chemistry, lipids, glucose, insulin, antinuclear antibodies (ANA), glycosylated hemoglobin A1c (HbA1c), urinalysis, human immunodeficiency virus (HIV), Hepatitis B and C, serum and plasma for biomarkers and a 12-lead electrocardiogram (ECG). A serum pregnancy test for women of child bearing potential (WOCBP) will be obtained at screening as well.
 
Blood samples for circulating proteins (serum and plasma) and for deoxyribonucleic acid (DNA) and ribonucleic acid (RNA) will be collected from each consenting patient, by signing off the additional research program part (optional) included in the main informed consent forms.
 
Safety assessments are done at each study visit and include AEs, serious adverse events (SAEs) and adverse events of special interest (AESIs) including but not limited to neutropenia, thrombocytopenia, elevations in hepatic enzymes leading to permanent discontinuation and TB, and potential opportunistic infections.
 
A dual assessor approach will be required in order to maintain the blind during the double-blind treatment period with sarilumab, placebo, and prednisone. Efficacy Assessor should be a rheumatologist or other skilled GCA assessor and may be the Principal Investigator; they will be responsible for completing the overall evaluation and management of GCA disease activity. The Safety Assessor should be a physician; they will be responsible for assessing and managing any safety concerns of the patient during the course of the study including access to the patient's laboratory data and AEs, performing assessments related to GTI. The

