- E 29. Patients with a history of a systemic hypersensitivity reaction, other than localized injection site reaction, to any biologic drug and known hypersensitivity to any constituent of the sarilumab product.
- E 30. Patients with any of the following laboratory abnormalities at the screening visit:
- Hemoglobin <8.5 g/dL.
 - White blood cells <3000/mm³.
 - Neutrophils <2000/mm³.
 - Platelet count <150 000 cells/mm³.
 - Aspartate aminotransferase (AST) or alanine aminotransferase (ALT) >1.5 x upper limits of normal (ULN), unless this is a manifestation of active GCA in the opinion of the Investigator.
 - Bilirubin (total) >ULN, unless documented Gilbert's disease diagnosed by genetic testing.
 - Presence of severe uncontrolled hypercholesterolemia (>350 mg/dL, 9.1 mmol/L) or hypertriglyceridemia (>500 mg/dL, 5.6 mmol/L).
 - Patients with a calculated creatinine clearance <30 mL/minute (using Cockcroft-Gault formula).

Note: Laboratory parameters may be repeated during the screening period if judged to be spurious or due to technical error in order to determine eligibility.

E 31. Patients with a history of inflammatory bowel disease or severe diverticulitis or previous gastrointestinal perforation.

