10.2.1 Visit 1: Screening from Day -42 to Day -1

The following activities will be performed:

- An explanation of the purpose, procedures, potential risks, and benefits of this study will be provided to the patient.

- Informed consent signature and date will be collected.
- If required locally, the locally provided consent for the required HIV screening test will be collected.
- Call IRT to assign patient number and register screening visit.
- Patient demography will be recorded.
- Medical/surgical/smoking/alcohol history.
- Review of prior and concomitant medication history.
- Family cardiovascular history.
- Full physical examination.
- GCA clinical assessments (including disease flare).
- Measure vital signs (including systolic and diastolic BP [mmHg], HR [beats per minute], body temperature [°C], and height [cm]).
- Body weight [kg].
- Perform blood sampling (fasting) for the following tests:
 - Hematology, chemistry.
 - Fasting lipids, fasting glucose and fasting insulin.
 - HbA1c.
 - CRP and ESR.
 - Virology.
 - Serum β -hCG pregnancy test (for WOCBP).
- Tuberculosis assessment including Quantiferon gold testing.
- Urinalysis (dipstick)
- 12-lead ECG.
- Perform chest X-ray if not performed at least 12 weeks prior to screening visit date.
- Confirmation of eligibility by the Investigator.
- Schedule a Visit 2 (D1, Week 0) within a maximum of 42 days from Visit 1.

Note: if the ultrasound is being used as a diagnostic tool for GCA to satisfy the Inclusion Criteria I01, the image needs to be submitted to the central reader for confirmation of eligibility.

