Appendix A Study flow chart

VISIT	V1	V2	V3	V4	V5	V6	V7	V8	V9	V10	V11	V12 (EOT)	V13	V14 (EOS)
DAY	D -42 to D -1	D1	D15 (±3)	D29 (±3)	D57 (±3)	D85 (±3)	D113 (±3)	D141 (±3)	D169 (±3)	D225 (±3)	D281 (±3)	D365 (±3)	D407 (±3)	D532 (±3)
WEEK		Wk 0	Wk 2	Wk 4	Wk 8	Wk 12	Wk 16	Wk 20	Wk 24	Wk 32	Wk 40	Wk 52	Wk 58	Wk 76
Eligibility														
Written informed consent	X													
Inclusion/exclusion criteria ^a	X ^a	X												
Patient demography	X													
Medical/surgical/smoking/alcohol history	X													
Prior medication history	X													
Family cardiovascular history	X													
Full physical examination	X											X		
Targeted physical examination ^b		X				X			X		X			
Confirm eligibility		X												
Randomization		X												
Call IRT	X	X	X	X	X	X	X	X	X	X	X	X		X
Treatment														
Initial treatment kit assignment (IRT)		X												
IMP administration ^c		X	X	X	X	X	X	X	X ^d	X ^d	X ^d	X		
Concomitant medication review	X	X	X	X	X	X	X	X	X	X	X	X	X	X
Dispense patient diary (for study medications)		X	X	X	X	X	X	X	X	X	X			
Compliance/review patient diary			X	X	X	X	X	X	X	X	X	X		

VISIT	V1	V2	V3	V4	V5	V6	V7	V8	V9	V10	V11	V12 (EOT)	V13	V14 (EOS)
DAY	D -42 to D -1	D1	D15 (±3)	D29 (±3)	D57 (±3)	D85 (±3)	D113 (±3)	D141 (±3)	D169 (±3)	D225 (±3)	D281 (±3)	D365 (±3)	D407 (±3)	D532 (±3)
WEEK		Wk 0	Wk 2	Wk 4	Wk 8	Wk 12	Wk 16	Wk 20	Wk 24	Wk 32	Wk 40	Wk 52	Wk 58	Wk 76
Vital signs														
Temperature, heart rate, blood pressure	X	X	X	X	X	X	X	X	X	X	X	X	X	X
Weight	X	X				X			X		X	X		
Height	X													
Efficacy														
GCA clinical assessments (including disease flare)	X	X	X	X	X	X	X	X	X	X	X	X	X	X
PROs ^e		X				X			X			X		
Physician Global Assessment (MD-VAS)		X				X			X			X		
GTI Assessment (excluding Bone Density assessment)		X				X			X		X	X		
Bone density assessment ^f		X										X		
Safety														
AE/SAE recording														
Tuberculosis assessment	X	X	X	X	X	X	X	X	X	X	X	X	X	
QuantiFERON®	X													
Chest X-ray ^g	X													
Laboratory testing														
Hematology ^h	X	X		X		X			X		X	X		
Chemistry ⁱ	X	X		X		X			X		X	X		
ANA		X										X		

VISIT	V1	V2	V3	V4	V5	V6	V7	V8	V9	V10	V11	V12 (EOT)	V13	V14 (EOS)
DAY	D -42 to D -1	D1	D15 (±3)	D29 (±3)	D57 (±3)	D85 (±3)	D113 (±3)	D141 (±3)	D169 (±3)	D225 (±3)	D281 (±3)	D365 (±3)	D407 (±3)	D532 (±3)
WEEK		Wk 0	Wk 2	Wk 4	Wk 8	Wk 12	Wk 16	Wk 20	Wk 24	Wk 32	Wk 40	Wk 52	Wk 58	Wk 76
Fasting lipids ^{j, k} /fasting glucose, fasting insulin ^j	X			X		X			X		X	X		

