Appendix H Visit windows based on day ranges

Visit windows based on days relative to the first IMP dose will be used to map (see [Table 9](#)).

Table 9 - Day range for each scheduled visit in the DB period for efficacy, lab, vital sign, PK and ADA summaries

Visit Label	Target Day	Schedule A ^a	Schedule B ^b	Schedule C ^c	Schedule D ^d	Schedule E ^e	Schedule F ^f	Schedule G ^g	Schedule H ^h	Schedule I ⁱ	Schedule J ^j
Double-Blind Period											
Baseline	1	≤1	≤ 1	≤ 1	≤ 1	≤ 1		≤ 1	≤ 1	≤ 1	≤ 1
Week 2	15	>1'- 21							>1'-21	>1'-49	
Week 4	29	22-42				>1'-56	>1'-56	>1'-42	22 - 56		>1'-98
Week 8	57	43-70						43 - 70			
Week 12	85	71-98	>1'-126	>1'-126		57 - 126	57 - 126	71 - 98	57 - 98	50 - 126	
Week 16	113	99-126						99 - 126	99 - 140		
Week 20	141	127-154						127 - 154			
Week 24	169	155-196	127 - 224	127 - 266		127 - 224	127 - 224	155 - 196	141 - 266	127 - 266	≥ 99
Week 32	225	197-252						197 - 252			
Week 40	281	253-322	225 - 322			225 - 322	225 - 322	253 - 322			
Week 52	365	≥323	≥ 323	≥ 267	>1'	≥ 323	≥ 323	≥ 323	≥ 267	≥ 267	

a Includes temperature, heart rate, blood pressure, GCA clinical assessments (including disease flare), CRP, ESR

b Includes weight, glucocorticoid toxicity index (excluding bone density assessment)

c Includes physician global assessments (MD-VAS), patient reported outcomes and antibodies to sarilumab/ADA

d Includes bone density assessment, ANA

e Includes hematology: hemoglobin, hematocrit, red blood cell (RBC) count and morphology (if RBC count is abnormal), white blood cell (WBC) differential, platelet count, absolute neutrophil count (ANC) and chemistry: sodium, potassium, calcium, chloride, bicarbonate, total protein, creatinine and clearance, blood urea nitrogen (BUN), uric acid, lactate dehydrogenase (LDH), phosphate, albumin, ALT (SGPT), AST (SGOT), alkaline phosphatase (ALP), total bilirubin, conjugated bilirubin, and unconjugated bilirubin

f Includes HbA1c, fasting glucose, fasting lipids: triglycerides (TG), total cholesterol, HDL, LDL

g Includes urine pregnancy test

h Includes serum sarilumab

i Includes biomarkers-IL-6 and sIL-6R

j Includes immune cell phenotyping (whole blood)

* Includes value measured on day 1 but after the first IMP dose

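### The midpoint rule for lipid onset times is not bounded at first dose, so an LDL-C or cholesterol elevation first seen at Week 4 can be dated before treatment began

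*SAP*

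**What the plan says.** SAP 2.4.5.3 lists several laboratory time-to-onset analyses, including LDL-C at two thresholds and "time to onset of the initial total cholesterol elevation (≥ 6.2 mmol/L"). All use Kaplan-Meier estimates, with onset dated "using the midpoint of the time interval between the first assessment showing the elevation and the previous assessment". The sentence gives no time origin, does not truncate at first dose and does not limit which assessments may serve as the previous one. The neighbouring sentences on PCSA incidence and shift tables refer to the TEAE period; this one does not.

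The lipid sampling schedule is set out in several places:

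- **Flow charts (protocol 1.2, SAP Appendix A).** The row "Fasting lipids ^{j, k} /fasting glucose, fasting insulin ^j" is marked at V1, V4, V6, V9, V11 and V12, and not at V2 or V3.
- **Protocol 10.2.1.** The Visit 1 blood list has "Fasting lipids, fasting glucose and fasting insulin", and the site is to "Schedule a Visit 2 (D1, Week 0) within a maximum of 42 days from Visit 1".
- **Protocol 10.2.2.1 and 10.2.2.3.** The Visit 2 blood list includes hematology and chemistry but no lipids. Lipids resume at Visits 4, 6, 9 and 11.
- **SAP Appendix H, Table 9.** Schedule F ("Includes HbA1c, fasting glucose, fasting lipids: triglycerides (TG), total cholesterol, HDL, LDL") has a blank Baseline cell.

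On entry, protocol E 30 excludes only "Presence of severe uncontrolled hypercholesterolemia (>350 mg/dL, 9.1 mmol/L") or marked hypertriglyceridemia.

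**The concern.** Protocol 11.4.3.2.2 applied the midpoint rule to ALT, AST and bilirubin only. These belong to the chemistry panel, which is drawn before dosing on Day 1, so the interval ending at Week 4 starts at first dose and its midpoint is post-dose. The SAP extends the rule to lipids, which have no Day 1 sample. The interval for a Week 4 elevation then reaches back into screening, and its midpoint can fall before the patient received any study drug.

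Protocol 8.8.3 says that anti-IL-6 drugs, sarilumab included, are known to raise total cholesterol and that the effect will be watched closely. Week 4 is the first scheduled post-dose lipid sample, so an early lipid rise would first appear in exactly the interval that the rule mishandles. A zero or negative time has no natural place on a curve that starts at first dose, and the SAP does not say what to do with one. A positive but shortened time would pass unnoticed.

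There is a second gap. A patient can enter above 6.2 mmol/L, because the cholesterol exclusion begins above 9.1 mmol/L. The SAP does not say how such a patient enters these curves.

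**Working it through.** The documents give no figure for this rule, so there is nothing to reproduce. The check is date arithmetic, in days from first dose.

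**Inputs**

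- First dose: Day 1, taken as time 0.
- Screening lipid sample: "Visit 1 (D -42 - D -1): Screening", that is k days before first dose with k = 1 to 42.
- Week 4 lipid sample: Day 29 ± 3 (flow charts), that is +28 days nominally and +25 to +31 across the window.

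**Formulas**

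- Onset under the SAP rule = (e - k)/2, where e is the day of the Week 4 sample.
- Onset with the left end bounded at first dose = e/2.
- Difference = e/2 - (e - k)/2 = k/2.

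**Results for an elevation first seen at Week 4**

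| Week 4 sample | Onset, k = 1 | Onset, k = 42 | Negative when | Screening days giving a negative time | Bounded midpoint |
|---|---|---|---|---|---|
| Day 26 (e = 25) | +12.0 | -8.5 | k ≥ 26 | 17 of 42 (40%) | +12.5 |
| Day 29 (e = 28) | +13.5 | -7.0 | k ≥ 29 | 14 of 42 (33%) | +14.0 |
| Day 32 (e = 31) | +15.0 | -5.5 | k ≥ 32 | 11 of 42 (26%) | +15.5 |

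At the nominal visit day, k = 28 gives exactly 0. For k below 28 the time is positive but still k/2 days earlier than the bounded midpoint. Over k = 1 to 42 the difference runs from 0.5 to 21 days. If screening days were evenly spread (an assumption; the documents do not give the actual gaps), the mean difference would be (1 + 42)/4 = 10.75 days.

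**Comparison with the other parameters.** ALT, AST, bilirubin, neutrophils, lymphocytes and platelets have a Visit 2 sample, so their nominal Week 4 midpoint is (28 + 0)/2 = +14 days. They are not affected.

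**Patients above threshold at entry.** Protocol 11.4.3 makes the TEAE period the observation period for safety analyses, and SAP 2.1.4 starts that period at first dose. A screening value is therefore not itself the event. The first post-dose sample still above the threshold is, so a pre-existing elevation would be counted as a new onset, typically at Week 4.

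**The case against.** **The SAP can be read as having a baseline lipid sample.** Section 2.1.4.3 classes fasting lipids under clinical chemistry and lists baseline among the chemistry collection times. That sentence yields where something else is specified, however. Both flow charts, the Visit 2 list and Table 9 treat lipids separately from chemistry and give no Day 1 sample. The section should be aligned with them; it does not remove the problem. A repeat or unscheduled lipid sample nearer Day 1 would shorten the gap, but none is required.

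**The previous assessment is not defined as including screening.** True, but if it had to be post-dose, a Week 4 elevation would have no previous assessment and the rule would give no date. Limiting events to the TEAE period does not help either, because it restricts the event and not the left end of the interval.

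**Stronger readings that a reader might infer.** Four are not supported:

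- *Patients above threshold at screening have no valid onset time.* The TEAE observation period makes the qualifying sample post-dose, so they get a date; the fault is that it counts as new.
- *Events with negative times are lost.* The SAP does not state how non-positive times are handled, so loss is possible but not shown.
- *Onset is wrong by up to 21 days.* With no sample between first dose and Week 4, the true onset is unknown within that interval, and +14 days is itself a convention. The 0.5 to 21 days is a distance from that convention.
- *The arms are biased against each other.* The screening gap is fixed before randomization, so no systematic difference in gaps between arms follows from the documents.

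**The information is available elsewhere.** This stands in large part. Appendix B uses the same cut-offs as PCSA criteria, 2.4.5.3 allows PCSA incidence and shift tables by baseline status, baseline lipids are classified by NCEP ATPIII, and means by visit and listings are unaffected.

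**Conclusion.** The point holds, and it is minor. As written, the rule places a lipid elevation first seen at Week 4 at (28 - k)/2 days: always earlier than the first-dose-bounded midpoint, and before first dose for 14 of the 42 permitted screening days (11 to 17 across the visit window). This assumes the scheduled samples only, with no unscheduled lipid sample between screening and Week 4. How many patients are affected cannot be said, because neither the actual screening gaps nor the numbers above threshold at entry are given.

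The damage is confined to placement within the first interval of these curves and to the counting of pre-existing elevations as new. Elevations first seen after a non-elevated Week 4 sample are dated normally. If the affected events are kept, cumulative incidence at Week 4 and later is unchanged, leaving aside any patient censored inside that first interval. The curves are descriptive, in a terminated study of 83 patients, and no endpoint, test or safety rule depends on the onset times.

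**What to change.** In SAP 2.4.5.3, for all the time-to-onset analyses:

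1. State that time zero is the first SC IMP dose.
2. Count only assessments after the first SC IMP dose as events.
3. Set the left end of the interval at the later of the previous assessment and the first SC IMP dose.
4. Restrict each curve to patients not already beyond the threshold at baseline, or show those patients separately; in either case give their number per arm.

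Also align SAP 2.1.4.3 with the flow chart and Table 9 on whether lipids are drawn at baseline.

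The cost is a few sentences of text and a small programming change. Under the restricted option, patients already above threshold leave the risk set. That is a small loss in arms estimated at 28, 14, 14 and 27 (SAP 1.3), and the per-arm counts make it visible.
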